**Research Questions:**

Does prone positioning increase the oxygen saturation of blood?

Does prone positioning have any effect on the severity of illness- if prone positioning has any benefits in terms of decreased severity of illness or in terms of decreased mortality at 3 months in patients with covid pneumonia?

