**Study Protocols:**

All the patients who are received in the medical emergency department as a suspected case of covid pneumonia/ acute respiratory distress syndrome (ARDS), will be assessed in the emergency department as per hospital protocols. If admitted for covid pneumonia/ ARDS, the patient will be offered to consent for participation in the study. The patients who themselves cannot consent due to severity of condition, the attendant closest in relation to the patient will be asked about the consent.

Patient will then be randomized through permuted block randomization into either a control or experimental group and shifted to the respective ward.

Complete data will be recorded on the questionnaire and will be considered as the day one of admission of the patient.

Patients in the prone position group will then be guided for prone positioning for eight hours of intermittent prone positioning. Each cycle may be from 30 minutes to 3 hours. Prone positioning was to be done under the supervision of the staff who were trained by the researchers. The prone positioning was to be done by patient him/herself after guidance with assistance if required so that patient is more comfortable.

Researcher will visit each patient twice a day to ensure if the patient was properly getting the prone positioning intervention and to assess if the patient can tolerate it. In case any complication happens due to the manoeuvre, it will be discussed with the lead investigator. The patient will be assessed for fitness to continue being part of the study or to withdraw from the study.

Record of the prone positioning cycles will be maintained by the staff in the patient file.

Seventh day will be the last day of prone positioning. Data will be recorded by the researcher on seventh day of admission at least ten minutes after the patient has been put to supine position.

Data will also be collected at 14th day of admission of the patient, if the patient is still in the ward.

Patient survival at 90th day will be confirmed by calling the patient/ attendant and requesting for death certificate in case the patient died after discharge from the facility.

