**Analyses:** Data will be analysed on SPSS version 25. Statistical tests will be applied to see effect of prone positioning on the severity of covid pneumonia and acute respiratory distress syndrome and to find out its effects on mortality and respiratory physiology – PaO2, respiratory rate and oxygen requirement as determined by the type of oxygen delivery mask, with a confidence interval of 95%. P value of <0.05 will be considered statistically significant. Data will be presented in tables, bar charts, and pie diagrams. Tests of significance will be applied to see effects of prone positioning on respiratory physiology and Kaplan Meier curve will be obtained to compare the survival of the two groups.

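### The respiratory analysis does not say which day is tested, makes no use of day-one values, gives no rule for patients lost before day 7, and leaves the saturation question without a matching analysis

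*Combined protocol and SAP*

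**What the plan says.** The first item under Research Questions is "Does prone positioning increase the oxygen saturation of blood".

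Under Study Protocols, patients are "randomized through permuted block randomization into either a control or experimental group and shifted to the respective ward". Three collections of physiology follow:

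- **Day one:** "Complete data will be recorded on the questionnaire and will be considered as the day one of admission of the patient". Instruction in proning comes after this in the text, so the day-one values precede the intervention.
- **Day 7**, the last day of proning: "Data will be recorded by the researcher on seventh day of admission", with the patient supine for a set minimum time beforehand.
- **Day 14**, but only "if the patient is still in the ward".

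The same section foresees patients leaving. After a complication of the manoeuvre, "The patient will be assessed for fitness to continue being part of the study or to withdraw from the study". A death certificate is to be requested "in case the patient died after discharge from the facility". After discharge, only survival is followed.

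Analyses lists the physiology outcomes as PaO2, "respiratory rate and oxygen requirement as determined by the type of oxygen delivery mask". It promises significance tests at 0.05 with 95% intervals, and a Kaplan-Meier curve for survival. For physiology it gives no day, no model, no role for day-one values and no rule for patients without a day-7 reading. It does not mention saturation.

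**The concern.** Four gaps meet in one analysis, and they are not equally serious.

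- **Day.** With day 7 and day 14 both collected and neither named, the choice can be made after the results are seen.
- **Day-one values.** They are collected but have no stated use. Allocation is randomised, so with complete data leaving them out causes no bias. It wastes precision that has already been paid for.
- **Patients without day-7 physiology.** This is the main issue. If no rule is written, the default is to test whoever has a reading. Death and discharge come after randomisation, and proning may alter both, so the remaining patients in the two arms need not be comparable. If proning keeps sicker patients alive, its survivors can look worse. If it sends fitter patients home sooner, those left in the ward can look worse too. The only withdrawal route described starts from a complication of the manoeuvre, so it bears on the prone arm.
- **Research question 1.** It asks about saturation, and no listed analysis answers it.

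**Working it through.** The sections reviewed give no sample size, SD, effect size or event rate, so there is no planned figure to reproduce. Apart from the 0.05 level (taken as two-sided), every input below is an assumption.

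**1. Cost of ignoring day one.** Let r be the correlation between the day-one and day-7 values. Variance relative to comparing day-7 values alone is 1 − r² for ANCOVA and 2(1 − r) for a change score.

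| r | ANCOVA | Change score | Unadjusted patients matching 100 adjusted, 100/(1 − r²) |
|---|---|---|---|
| 0.3 | 0.91 | 1.40 | 110 |
| 0.5 | 0.75 | 1.00 | 133 |
| 0.7 | 0.51 | 0.60 | 196 |

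ANCOVA is the most precise of the three approaches at each of these correlations.

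**2. False effect from testing survivors only.** Assume:

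- log PaO2/FiO2 is normal with SD 0.4 and the same mean in both arms, so there is no oxygenation effect;
- 100 patients per arm;
- 25% of controls and 15% of proned patients die before day 7;
- death falls on the lowest values of a score that correlates ρ with the log ratio.

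The mean of a standard normal variable above its p-th quantile z is φ(z)/(1 − p). This is 0.424 for p = 0.25 and 0.274 for p = 0.15. The survivors' difference, prone minus control, is therefore 0.4 × ρ × (0.274 − 0.424) = −0.060ρ.

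| ρ | Log difference | Ratio of PaO2/FiO2, prone to control | Trials showing significant harm |
|---|---|---|---|
| 1 | −0.060 | 0.94 (6% lower) | about 23% |
| 0.7 | −0.042 | 0.96 (4% lower) | about 12% |
| 0.5 | −0.030 | 0.97 (3% lower) | about 8% |

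The last column comes from simulated t tests. A normal approximation with 75 v 85 survivors gives 23%, 11% and 7%. With no selection, chance gives 2.5%.

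**3. Shrinkage of a real effect.** Now let proning raise the log ratio by 0.20 (a factor of 1.22). Apply the same exit cut-offs to both arms, set so that 25% of controls are discharged and 15% die before day 7. With complete data, 0.20/(0.4 × √(2/100)) = 3.54, and power is Φ(3.54 − 1.96) = 94%. Among patients still in the ward:

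| ρ | Log difference | Power |
|---|---|---|
| 1 | 0.04 | about 23% |
| 0.7 | 0.12 | about 56% |
| 0.5 | 0.16 | about 68% |
| 0 | 0.20 | about 78% |

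The difference shrinks but stays positive throughout.

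**4. Counting everyone on the mask scale.** In the model of step 3, FiO2 is the lowest step that brings PaO2 to at least 70, over six assumed lists of mask steps. Power for mask type:

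| ρ | Ward patients only | All randomised, discharge best and death worst |
|---|---|---|
| 1 | 17–22% | 90–91% |
| 0.7 | 46–52% | 78–81% |
| 0.5 | 56–64% | 63–68% |
| 0 | 66–75% | 18–23% |

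The extended scale gains clearly when exits track oxygenation, is about level at 0.5, and loses when exits are unrelated to it.

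**The case against.** Much can be said for the plan, and some stronger readings should be set aside.

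- **No measurement day at all.** This would be wrong. Study Protocols fixes a standardised supine reading on the last day of proning and makes day 14 conditional, so day 7 is the natural choice. What stands is that Analyses does not commit to it.
- **The plan restricts the test to ward patients.** It does not say so; it is silent. Early exit is also partly inferred: the still-in-ward condition attaches to day 14, and the remark on death after discharge belongs to the day-90 follow-up. Withdrawal during the seven days of proning is foreseen directly. Deaths and discharges in that week are plausible, but their rates are assumed.
- **Selection reverses a real benefit.** The calculations do not show this. The false-harm scenario starts from no oxygenation effect, and the real-effect scenario shrinks without changing sign. The 23% is the extreme case of perfect correlation.
- **Ignoring day one biases the comparison.** With complete data it does not.
- **PaO2 is uninterpretable without the oxygen given.** A ratio of 150 does give PaO2 of 60, 90 or 120 mmHg at FiO2 of 0.4, 0.6 or 0.8. But mask type is already a planned outcome, and nothing says the two will be read apart. The documents do not describe how oxygen is adjusted. In the model above, with complete data, mask type alone has 87–93% power. This part is a reporting refinement.
- **Saturation is not collected.** That cannot be concluded, because the questionnaire is not part of the text. Only the absence of a named analysis is established.

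**Conclusion.** The point holds as a gap in specification that should be closed before the arms are compared. The text establishes four things: no named analysis day, no use of day-one values, no rule for patients without day-7 physiology, and no analysis matched to research question 1.

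The day-one omission costs precision only. The missing exit rule is the serious part, because a comparison of remaining patients can hide a real effect or create a false one. Its size depends on how strongly early exit tracks oxygenation, how far exit rates differ between arms, and how many patients are enrolled. The documents supply none of these. The figures show that the problem can be material; they do not predict this trial's result.

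**What to change.** Add the following to Analyses:

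1. Name day 7 as the analysis day for the physiology outcomes.
2. Compare arms by ANCOVA adjusted for the day-one value of the same measure (ordinal regression for mask type), and report the adjusted effect with its 95% CI.
3. Make day-7 oxygen requirement by mask type the principal oxygenation outcome, counting all randomised patients. Discharge by day 7 is the best category; death by day 7, including death after discharge, is the worst.
4. Analyse patients who stop proning or withdraw in their randomised arm, using day-7 data where available. Otherwise treat them as missing, with a sensitivity analysis.
5. Report deaths, discharges and withdrawals before day 7 by arm. Label the PaO2 and respiratory-rate results as applying to patients with day-7 data; ANCOVA does not remove that selection.
6. Report PaO2 together with the oxygen given, for example PaO2/FiO2 from one fixed mask table used in both arms, as supportive only.
7. Analyse saturation for research question 1 or, if it is not recorded, reword the question to PaO2.

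The cost is mostly wording, and SPSS fits these models. A few questionnaire fields may be needed: discharge date, saturation, and flow or FiO2. The Kaplan-Meier curve already requires dates of death.

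There are two statistical downsides. The extended mask scale loses power if early exits are unrelated to oxygenation (18–23% against 66–75%). FiO2 inferred from mask type is approximate: a log-scale error SD of 0.2 or 0.3 raises the total SD from 0.40 to √0.20 = 0.447 or √0.25 = 0.50, and power for the ratio with complete data falls from 94% to about 88% or 80%.

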**Objectives:**

To assess the efficacy and effects of prone positioning on the respiratory physiology and death rate of patients suffering from covid pneumonia/ acute respiratory distress syndrome.

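### Oxygen requirement is defined by mask type alone, with no stated level for patients off oxygen or ventilated; if only masked patients are scored, a benefit can be diluted, hidden or sometimes reversed

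*Combined protocol and SAP*

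**What the plan says.** The Analyses section of the combined protocol and SAP names three respiratory measures: PaO2, respiratory rate, and "oxygen requirement as determined by the type of oxygen delivery mask". That is the whole definition of the third. No mask types are listed or ordered. The test is not named either: "Tests of significance will be applied to see effects of prone positioning on respiratory physiology".

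The population is "patients suffering from covid pneumonia/ acute respiratory distress syndrome" (Objectives). Study Protocols provides for consent by a relative, with the wording "The patients who themselves cannot consent due to severity of condition", so some participants are severely ill at entry. Patients are "randomized through permuted block randomization into either a control or experimental group".

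On timing, Study Protocols states "Data will be recorded by the researcher on seventh day of admission", with no rule for patients who by then are off oxygen, ventilated, discharged or dead. Day 14 data are limited to patients who remain in the ward. Data collecting tool describes the questionnaire by demographics and pneumonia severity index parameters and mentions no categories of respiratory support. Mortality is handled separately, by a Kaplan-Meier comparison and a survival check at day 90.

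**The concern.** An intubated patient and a patient breathing room air have one thing in common: neither wears an oxygen mask. They are also the two ends of the outcome. Under Research Questions the trial asks whether proning makes the illness less severe, and coming off oxygen or going onto a ventilator are among the clearest changes in severity it could observe.

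The definition can be applied literally in two ways:

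- **Only masked patients are scored.** Being on a mask at day 7 is a state reached after randomisation, and proning may affect it. The two groups compared are then no longer the randomised groups.
- **Everyone without a mask gets one code.** Nobody is lost, but the best and worst survivors are counted together, and a difference in that code cannot be interpreted.

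A related gap affects PaO2 and respiratory rate. Any reading taken from a ventilated patient largely reflects the ventilator settings, and the plan has no rule to separate it from a spontaneous reading.

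**Working it through.** The document gives no sample size, event rate or effect size, so there is no figure of its own to reproduce. All counts below are assumptions chosen to show the mechanism.

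**Step 1. Simple case, survivors only, per 100 patients at day 7.**

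| | Ventilated | Highest mask | Lower mask |
|---|---|---|---|
| Control | 20 | 20 | 60 |
| Prone | 10 | 30 | 60 |

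Proning has halved ventilation and made nobody worse. Share of masked patients on the highest mask:

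- Control: 20/(20 + 60) = 20/80 = 25.0%
- Prone: 30/(30 + 60) = 30/90 = 33.3%
- Difference: 8.3 points against proning. With ventilation on the scale, proning is 20 − 10 = 10 points better in the worst category.

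If the 10 averted patients instead spread in proportion over the mask types (2.5 highest, 7.5 lower), the prone share is 22.5/90 = 25.0%. The benefit then disappears from view.

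**Step 2. Six states.** Assumed control distribution: off oxygen 20%, low-flow 20%, simple mask 20%, high-concentration mask 15%, ventilated 15%, dead 10%. The measure is P(prone patient better) + 0.5 × P(tie); above 0.5 favours proning. Mask-only scoring keeps the middle three states: 55% of controls, leaving out 45%.

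Suppose proning moves a share x from low-flow to off oxygen, and x from ventilated or dead to the high-concentration mask. At x = 10% the prone distribution is 30/10/20/25/9/6%.

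- All six states: [30×90 + 10×70 + 20×50 + 25×32.5 + 9×17.5 + 6×5]/10,000 = 5,400/10,000 = 0.540
- Masked only: [10×45 + 20×25 + 25×7.5]/(55×55) = 1,137.5/3,025 = 0.376

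| Assumed benefit | Full scale | Mask only |
|---|---|---|
| Both ends, x = 2% | 0.508 | 0.475 |
| Both ends, x = 5% | 0.520 | 0.438 |
| Both ends, x = 10% | 0.540 | 0.376 |
| 10% averted from ventilation or death, spread proportionally | 0.550 | 0.500 |
| Uniform, proportional odds, OR 1.25 to 3 | 0.536 to 0.668 | 0.518 to 0.583 |
| Within mask types only | 0.526 | 0.587 |

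The rows show, in order, reversal (three rows), loss of the effect, dilution, and exaggeration in the right direction.

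**Step 3. Shared no-mask code, x = 10%.** Control: 20 + 15 = 35%. Prone: 30 + 9 = 39%. Ten points more off oxygen and six points fewer ventilated appear as a rise of 39 − 35 = 4 points in one code with no clear meaning.

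**Step 4. Would a scale ending at ventilation be enough?** Assume per 100: control 20 dead and 10 ventilated; prone 10 dead and 20 ventilated. Among survivors, 10/80 = 12.5% of controls and 20/90 = 22.2% of prone patients are in the worst category, although deaths were halved. The same selection returns one level up, so death has to be on the scale.

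**The case against.** The strongest reply is that the plan does not say anyone is left out. The questionnaire's items are not shown, the mask levels are not listed, and mask type may be shorthand for delivery device, with entries for none and for ventilator. That stands. A reader might infer that the measure has no place for these patients and drops them; the documents support only that no place is stated.

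A reader might also infer that proning would generally look harmful. The working does not support that. Reversal needs the benefit to be concentrated at the ends of the scale; a uniform benefit keeps its direction, and so does a benefit confined to mask types.

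Nor do the documents show that ventilated patients stay in the ward and have PaO2 and respiratory rate recorded there. Ventilation is never mentioned, proning is performed by the patient with help if needed, and day 14 data depend on still being in the ward. Ventilated patients may be transferred and recovered ones discharged. This limits the claim about ventilator readings to a possibility. It does not remove the main problem, because such patients would be missing from the mask comparison for reasons tied to the outcome.

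Finally, mask type is one of three respiratory measures, and severity and survival are analysed separately. Deaths are therefore not hidden from the trial as a whole. The survival analysis does not, however, recover ventilation or weaning among survivors.

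**Conclusion.** The concern holds in limited form. Oxygen requirement rests on mask type alone, and the plan states neither its levels nor how to score patients who are off oxygen, ventilated, discharged or dead at the assessment days. If only masked patients are scored, the comparison is conditioned on a post-randomisation state and can be wrong in size or direction: 8.3 points of apparent harm or no difference in the simple case, and 0.376 against 0.540 in the most marked six-state case. If a single no-mask code is used, opposite outcomes are merged.

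These sizes rest entirely on assumed distributions. They show what can happen, not what will. How far the trial is exposed depends on the unseen questionnaire and on how many patients are off oxygen or ventilated by day 7. The change is worth making because the outcome bears directly on the trial's severity question and the remedy is cheap.

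**What to change.** In Analyses, replace mask type with one ordered respiratory-support scale:

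1. discharged or on room air;
2. each cannula or mask type in use at the hospital, in order of intensity;
3. non-invasive or high-flow support;
4. invasive ventilation;
5. death, as the worst level.

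Score every randomised patient at day 7, and again at day 14 with discharged and dead patients assigned their level rather than omitted. Compare the arms with a rank test or a proportional-odds model, and name which. Report the number ventilated by arm beside the PaO2 and respiratory-rate results, so that readings taken on a ventilator are not read as spontaneous values. Giving ventilated patients the worst rank on those two measures is possible, but it is one option among several and turns them partly into measures of ventilation.

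The cost is a few extra questionnaire categories, some follow-up of patients who have left the ward, and an ordinal result in place of a simple mask table. Data collection procedure already draws on the medical record, though the document does not say that support status is held there. Patient care is unchanged.

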**Data collecting tool:**

A self-developed, structured questionnaire. The questionnaire includes socio-demographic data of patients along-with parameters of pneumonia severity index.

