**Data collection procedure:**

A structured questionnaire is developed and is tested before adopting the final version. Informed consent will be obtained from all the patients prior to inclusion in the study as a part of ethical practice. Data will be collected regarding personal profile/ demography of the patient by interviewing them, detailed history and thorough clinical examination and relevant investigations. Data will be collected from their medical record book/ file as well.

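### PaO2 and mask type are compared between arms without the oxygen given being fixed or stated to be recorded, so neither can be read cleanly as an effect on the lungs

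*Combined protocol and SAP*

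**What the plan says.** The Analyses section of the combined protocol and SAP names three respiratory measures: PaO2, respiratory rate and "oxygen requirement as determined by the type of oxygen delivery mask". It adds that "Tests of significance will be applied to see effects of prone positioning on respiratory physiology", with significance at p<0.05. It does not relate PaO2 to inspired oxygen and does not list saturation, although the first item under Research Questions is "Does prone positioning increase the oxygen saturation of blood".

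Study Protocols gives one measurement condition, for day 7: readings are taken "at least ten minutes after the patient has been put to supine position". That fixes posture, not oxygen. The same section says "Prone positioning was to be done under the supervision of the staff who were trained by the researchers" and has staff log the cycles in the patient file, so those giving care know who is being proned. For day 1, after describing randomisation and transfer, it says "Complete data will be recorded on the questionnaire and will be considered as the day one of admission of the patient". Guidance on proning comes next in the text. Day 14 is recorded only for patients still on the ward.

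On the form, Data collecting tool says "The questionnaire includes socio-demographic data of patients along-with parameters of pneumonia severity index". Data collection procedure adds "Data will be collected from their medical record book/ file as well".

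**The concern.** A PaO2 value means little without the oxygen the patient was breathing when it was taken, and a mask is chosen by a clinician. Both move with need, and both also move with how readily staff step oxygen up or down. Oxygen is adjusted after allocation, so randomisation does not balance that decision between arms.

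Two things are at stake.

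- **PaO2.** If proning helps and staff respond by reducing oxygen, the benefit is partly or wholly removed from PaO2. A test on raw PaO2 could then show nothing, or a result in the wrong direction.
- **Mask type.** If staff step one arm down sooner, or hold it on larger masks for longer, at equal need, the comparison picks up practice as well as physiology. That could create an apparent effect or conceal a real one.

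**Working it through.** The plan gives no sample size, mask distribution, named test or oxygen practice, so there is no figure to reproduce. Every numerical input below is an assumption.

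**1. Reading the text.** From Objectives to Analyses there is no saturation target, no step-up or step-down rule, and no flow or inspired-oxygen setting. The one reference to hospital protocols concerns emergency department assessment before randomisation.

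**2. PaO2.** Approximation: PaO2 = ratio × inspired oxygen. Lower inspired oxygen from 0.6 to 0.5 with no change in the lungs:

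| Ratio (mmHg) | PaO2 at 0.6 | PaO2 at 0.5 | Fall |
|---|---|---|---|
| 100 | 60 | 50 | 10 |
| 150 | 90 | 75 | 15 |
| 200 | 120 | 100 | 20 |

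PaO2 breaks even when the ratio rises by 0.6/0.5 = 1.2, a 20% gain. Starting at 150, a patient who improves to 150 × 1.2 = 180 has PaO2 = 180 × 0.5 = 90, the same as before (150 × 0.6 = 90). A smaller gain leaves PaO2 between 75 and 90, which is lower than at the start despite better lungs.

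So a lower mask with a lower PaO2 fits either a partial benefit or a step-down by habit. Inspired oxygen separates them: 75/0.5 = 150 is no change, and 90/0.5 = 180 is a 20% gain.

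**3. Mask type, false positives.** Assume five levels with shares 0.25/0.20/0.20/0.25/0.10 from lowest to highest, equal need in both arms, and a tie-corrected Mann-Whitney test at two-sided 0.05, with 20,000 simulated trials per setting. A fraction q of prone-arm patients above the lowest level is moved down one level by habit alone. Since 1 − 0.25 = 0.75 are above the lowest level, q = 20% moves 0.20 × 0.75 = 15% of the arm. The table gives rejections in either direction:

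| Per arm | q = 0 | 5% | 10% | 20% |
|---|---|---|---|---|
| 30 | 4.9% | 5.0% | 5.4% | 7.3% |
| 50 | 4.9% | 5.2% | 5.9% | 8.2% |
| 100 | 5.0% | 5.7% | 6.8% | 12.6% |
| 200 | 5.1% | 6.1% | 8.8% | 20.2% |

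Across four mask distributions, with 100 per arm and q = 20%, the rate is 9% to 17%.

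**4. Mask type, hidden benefit.** Suppose proning truly moves 40% of prone-arm patients above the lowest level down one level, and a fraction q of the prone arm is then kept one level higher by habit. Power, counting only results that favour proning:

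| Per arm | q = 0 | 5% | 10% | 20% |
|---|---|---|---|---|
| 100 | 36% | 27% | 19% | 8% |
| 200 | 62% | 48% | 35% | 13% |

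The tables in steps 3 and 4 count different events and should not be compared with each other.

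**5. A second model.** Treat mask type as high or low, with 50% high in controls. A 10-point shift from practice alone gives a significant result favouring proning in 17%, 29% and 52% of trials with 50, 100 and 200 per arm. A 5-point shift gives 7%, 11% and 17%. The mechanism does not depend on one model, but the size does.

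**The case against.** The strongest reply is that this is a possible bias and not a demonstrated one. It applies to any unblinded trial with an outcome that depends on care, and the larger figures need about one in five eligible prone-arm patients to be moved by habit with nothing comparable among controls. That stands. With habits of 5% to 10%, the false-positive rate is 5% to 7% at 30 to 100 per arm and at most 9% at 200.

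Part of the remedy may already be in hand. Saturation is the subject of a research question, the patient file is a data source, and the questionnaire itself was not available, so saturation or flow may be fields on it. Some opening pages were also unavailable. This too stands: the point is that the available text does not state the recording, not that the data are absent. The analysis named for PaO2 is still on the raw value.

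It can be said that PaO2 already checks the mask outcome, because a mask lowered by habit alone would tend to come with a lower PaO2. This stands only in part. Step 2 shows that a partial benefit gives the same pattern, and the use of file data means the two readings need not be simultaneous.

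Three stronger readings are tempting, and the documents do not support them.

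- A reader might infer from the wording on transfer after randomisation that the arms are in separate wards under different staff. The text says nothing on staffing and does not establish separate wards.
- A reader might infer that the day-1 record is equally exposed because it follows randomisation in the text. Patients share a common emergency pathway, the record precedes guidance on proning, and there has been little time for practice to diverge. Day 1 is much less exposed.
- A reader might extend the point to mortality. Survival at 90 days is not measured through the mask.

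**Conclusion.** The point holds as an inexpensive improvement to the method, with medium confidence. Two of the three named respiratory measures move with the oxygen that staff who can see the allocation choose to give, and the plan as available neither fixes that oxygen nor states that it is recorded with them.

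The PaO2 part needs no difference in practice between arms. Appropriate step-down in response to real improvement is enough to shrink, cancel or reverse the raw PaO2 difference. The 10 to 20 mmHg illustration rests on a constant ratio of 100 to 200 mmHg and a step from 0.6 to 0.5.

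The mask part is conditional on practice differing between arms, which the documents do not show. Its true size is unknown. In the illustrations it runs from negligible, for a rare habit or a small trial, to a 20% false-positive rate with 200 per arm and a 20% habit. The exposed readings are days 7 and 14.

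**What to change.** 1. **Recording.** At day 1, day 7 and day 14, record mask type, flow (or estimated inspired oxygen), saturation and any PaO2 at the same moment.
2. **Analyses.** Analyse PaO2 relative to inspired oxygen, and report saturation by arm beside mask type. Include every patient with a record, and do not exclude those off target. Treat a saturation difference within a mask type as a flag only: mask type is set after randomisation, and a real benefit can also produce such a difference.
3. **Study Protocols.** State that both arms follow the same saturation target and the same step-up and step-down rule. If the hospital has its own rule, citing it is enough; otherwise the investigators should name one.

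The cost is a few form fields, if they are not already there, and a short instruction to ward staff. No extra patients or visits are needed. Inspired oxygen is only approximate on masks, and some staff discretion remains, so this reduces the problem without removing it. In the step 3 illustration with 100 per arm, if the rule cut a 20% habit to 5% (itself an assumption), the false-positive rate would fall from 13% to 6%. Patients no longer on the ward at day 14 are a separate matter that this change does not address.
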